6.1.2 COLUMBIA-SUICIDE SEVERITY RATING SCALE (C-SSRS)

The C-SSRS is a rater-based interview to assess the severity and intensity of suicidal ideation and behaviors. Results will be presented for each question and within each of four constructs using counts and percentages over time: at week 4, week 8, and week 12.

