B.2.5. Secondary Endpoints. Diagnostic interviews will be conducted with each participant with the **Mini International Neuropsychiatric Interview Neurocognitive for Children and Adolescents (MINI-KID)**, a widely used, structured diagnostic interview that will be used to verify diagnosis at the screening visit (Sheehan et al 2010). Secondary endpoints will consist of the following measures, assessed using a within-group comparison, over time: **1) Suicidal ideation.** The Suicide Ideation Questionnaire (SIQ) is a 30 – item self or clinician administered instrument used to measure the current intensity of patients' specific distress and suicidal intent, which has been validated for use with adolescents (Pinto et al 1997). Score range is 0-180, with higher score indicating higher intensity. **2) Suicide attempts and other behaviors.** This outcome will be assessed via the Columbia Suicide Severity Rating Scale (CSSRS), which was designed to classify suicide attempts, aborted suicide attempts, and other suicidal behaviors and has been validated for use with adolescents (Gipson et al 2015). **3) Depressive symptoms.** The Patient Health Questionnaire (PHQ-9) is a 9-item self-report form to assess the severity of depressive symptoms that has been widely used in practice and research and validated for use with adolescents. This will be used throughout the study to assess severity of any depressive symptoms each subject is experiencing (Richardson et al 2010).

B.2.6. Participant Remuneration for follow-up sessions. All participants will be paid \$20 for completing each post-discharge assessment (weeks 1, 4, 8, 12, and 16; \$100 total) and a \$25 bonus for completing all assessments. Adolescents and parents/guardians will be paid separately, with separate ClinCards, for their participation (maximum \$125 each). Data from parent/guardians will continue to be collected in cases where participants reach age of maturity during study participation so long as the child continues participation in the study as an adult (i.e., signs adult informed consent form). Parent/guardian date of birth is required in order to register the ClinCards to the parent/guardian. This information will be collected during the consenting process. Payments will not be prorated for partial completion of assessments. Sufficient funding has been budgeted for this portion of the project (see Budget Justification).

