B.2.11. Rationale for Number of Subjects. We will recruit 20 youth age 13-17 years who complete enrollment in the [REDACTED] app. Expecting 10% attrition rate before completing enrollment in the [REDACTED] app we will consent 22 youths to reach our target enrollment number of 20. Means, medians, ranges, and standard deviations for the length of time taken for patients to work through the intervention and for patients to complete the eligibility interview, baseline, post-treatment (8 weeks) and follow-up (12 and 16 weeks) assessments will be reported. In addition, means and SDs will be reported for the length of time it takes project personnel to administer the data collection procedures from invitation through treatment. These data will be used to assess the feasibility of the intervention and study procedures. They will also be used for formal power calculations to design an adequately powered RCT in a subsequent project.

TIMELINE

	Screening Period ^{a, f}	App Testing Period					Follow-Up Period	
Week(W)	W0	W1 ^b	W1-3	W4 ^b	W5-7	W8 ^b	W12 ^b	W16 ^b
Informed Consent	X							
Participant Information Sheet ^c	X							
Medications at Discharge (from medical record)	X							
Medication history form (parent report)		X		X			X	X
Research team phone call with outpatient provider		X						
Enrollment in [REDACTED]	X							
Mini-international neuropsychiatric interview (MINI-KID)	X							

Health Screen Interview	X							
Suicide Ideation Questionnaire (SIQ)	X	X		X		X	X	X
AE Assessment)	X	X		X		X	X	X
Patient Health Questionnaire (PHQ-9)	X	X		X		X	X	X
Columbia Suicide Severity Rating Scale (C-SSRS) - lifetime	X							
Columbia Suicide Severity Rating Scale (C-SSRS) – since last contact		X		X		X	X	X
Frequency of Use of App ^d		X	X	X	X	X	X	X
Interviews for feedback [REDACTED]		X		X		X	X	X
Utility of Techniques		X		X		X	X	X
Usability and Acceptability ^e		X		X		X	X	X
Assessment of healthcare resource utilization (parent report)		X		X		X	X	X

a Screening will be conducted while adolescent patients are at an inpatient psychiatric facility.

b Over the phone with member of the research team

c Sheet to collect demographic and contact information

d Unique logins and duration of each login

e System Usability Scale

f Visit 0 may take place over multiple sessions

RECRUITMENT AND RETENTION PLAN

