Enrollment Procedures. Eligible participants will be identified through medical record review. Consultations will be completed with participant's attending psychiatrists to confirm eligibility. Attending psychiatrists will be asked to inform the parent and patient that they will be contacted by staff about a research study; however, only IRB-approved study staff (without a treatment relationship with the patient) will recruit participants. When possible, parents and participants will be invited to participate in the study together. However, given that participants are inpatients and housed separately from parents, in most cases parents and patients will be invited to participate separately. When parents are not on site, IRB staff will call parents to invite them to participate. If parents agree, a remote consenting procedure will occur. Patients will all provide assent in person. Behavioral observations will be used as an additional indicator of assent. If patient's behavior does not indicate assent (e.g., avoiding eye contact, withdrawn) the participant will not be enrolled. Participants will not be recruited on the patient's first day of admission.

Retention Methods. We recognize that obtaining follow-up data is critical. Therefore, we will take several steps to optimize our ability to collect such data. During the informed consent process, participants (parents/guardians) will be asked to provide multiple forms of contact including a direct telephone contact and e-mail as well as the back-up numbers of at least two family members or friends in case study staff are unable to reach the participant at the direct number. If study staff is unable to reach the participant for follow-up at all contact numbers provided following no less than three call attempts, then a letter will be sent to the participant requesting that they contact the study staff. If no reply is received from 1 week of mailing the first letter, then a second letter will be sent requesting that the participant contact the study staff and also indicating a date by which study staff will no longer contact them to schedule follow-up calls. If no reply is received by the indicated date, then the participant will be considered lost to follow-up and will be withdrawn from the study.

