Risk Management. Suicidal ideation/behaviors will be assessed during each study interview (Week 0, Week 1, Week 4, Week 8, Week 16). Week 0 is the study baseline assessment, which occurs while the participant is housed in an inpatient treatment facility. For purposes of risk management, results of the study assessment at Week 0 will be shared with the inpatient treatment team in order to provide information relevant to their treatment/discharge planning. Remaining assessments are conducted by phone. In order to facilitate risk management during these calls we will do the following: 1) only enroll participants who provide assent/consent for the study to release information to their parent/guardian (note a parent/guardian interview is also routinely completed at this time), 2) only enroll participants who provide assent/consent for the study to release information to their outpatient provider (note that provider information may not be known at the time of consent in which case authorization will be obtained at the earliest possible time after provider information is known prior to making the initial outpatient provider call), 3) obtain location information at the start of each phone assessment, and 4) schedule phone assessments at a time when the parent/guardian is present at the same location as the participant. In addition to the routine outpatient provider call at week 1, increases in suicide risk will be communicated to the parent/guardian and outpatient provider. Details of study assessments indicating changes (i.e., increases) in risk since the previous assessment will be shared with the parent/guardian and outpatient provider. In addition, interviewers will engage in risk management interventions as clinically indicated following the guidelines outlined in the Risk Management Documentation Form. For patients scoring in the moderate or high-risk categories, a follow-up contact will be made with the parent/guardian and/or outpatient provider within 48 hours of the study call to assess follow-through with risk management recommendations provided by the study clinician. Participants will be informed that information they input to the app is not monitored for purposes of risk assessment.

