AE Reporting. Adverse events (AEs) will be monitored and documented at each study visit. Reporting of AEs will follow the Hartford HealthCare Institutional Review Board Policy 910 and NIMH policy. Given that all enrolled participants will have a history of suicidal ideation with plan, AEs related to suicidal thoughts/behaviors, including death by suicide, will be categorized as "expected". Further, AEs meeting any of the following criteria will be categorized as "Serious": results in death; is life-threatening (places the subject at immediate risk of death from the event as it occurred); requires inpatient hospitalization or prolongation of existing hospitalization; results in a persistent or significant disability/incapacity; results in a congenital anomaly/birth defect; an important medical event, based upon appropriate medical judgment, may jeopardize the subject's health and may require medical or surgical intervention to prevent one of the other outcomes listed in this definition; or results in a severely debilitating situation for the subject, such as psychological distress, financial hardship or damaging impact on social standing or employability. AEs which are unexpected, related, and serious will be reported to the HHC IRB within 7 calendar days and to the NIMH PO within 10 business days. Death related to the study will be reported to the NIMH PO within 5 business days. All other AEs will be documented and reported to HHC IRB and NIMH PO at the time of the respective annual progress reports.

OUI's DATA SECURITY AND RESOURCE SHARING PLAN

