2 SAMPLE SIZE

As proposed in the Phase 1 study, we will enroll 20 participants.

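### The suicidal-behaviour endpoint rests on the C-SSRS alone, so a suicide death, or a documented attempt with no later C-SSRS, would reach the AE/SAE tables but not the endpoint result

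*SAP*

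**What the plan says.** Protocol B.2.5 lists suicide attempts and other suicidal behaviour as a secondary endpoint: "This outcome will be assessed via the Columbia Suicide Severity Rating Scale (CSSRS". No second source is named. The Protocol timeline places the since-last-contact form at weeks 1, 4, 8, 12 and 16, by telephone.

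SAP 6.1.2 states: "The C-SSRS is a rater-based interview to assess the severity and intensity of suicidal ideation and behaviors". It plans counts and percentages for each question and within each of four constructs at weeks 4, 8 and 12. It gives no denominator, no rule for death or a missed interview, and no summary of any event over the whole follow-up.

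Other parts of the plan bear on the same events:

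- Protocol, AE Reporting, foresees adverse events of suicidal thoughts or behaviour, up to and including death by suicide. It treats death and inpatient hospitalization as serious.
- SAP 5.1 and 5.2 tabulate adverse events by system organ class and preferred term, with no link to SAP 6.1.2.
- Protocol, Retention Methods: after failed calls and two letters, "the participant will be considered lost to follow-up and will be withdrawn from the study".
- Protocol, Early Withdrawal of Participants: an attempt does not by itself end participation, but the site PI may withdraw a youth who is adversely affected by the app content.
- Protocol, Timeline and Risk Management: parents report healthcare use and are interviewed at the calls, and outpatient providers are contacted. None of this is said to feed the suicidal-behaviour endpoint.

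**The concern.** An endpoint on suicidal behaviour should count the gravest form of it. A youth who dies by suicide cannot give a further C-SSRS. A youth who makes an attempt after the last completed interview and is then withdrawn or lost has no C-SSRS that records it, even if the trial learns of it another way. The report could then list a suicide death as a serious adverse event while the suicidal-behaviour table shows no event for that participant.

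This matters beyond the small sample. Effects on suicidal ideation and behaviour are the secondary objective (Protocol B.2.1), and safety is part of the SAP's primary objective (SAP 1.1.1). Protocol, Innovation, says that suicide attempts are to be the primary outcome of the next line of research, so the way the event is ascertained here is likely to carry forward.

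**Working it through.** **The plan's own figure.** The plan states no expected rate of suicidal behaviour, so there is none to reproduce. Its only attrition figure is 10% before app enrollment (Protocol B.2.11): "we will consent 22 youths to reach our target enrollment number of 20". This reproduces as 20 × 1.10 = 22; dividing gives 20/(1 − 0.10) = 22.2. It says nothing about loss during follow-up.

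**Step 1. Where each event lands under the plan as written.**

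| Situation | C-SSRS record | SAP 6.1.2 table | AE/SAE tables |
|---|---|---|---|
| Attempt reported at a completed week 4, 8 or 12 interview | yes | counted | yes, if recorded as an AE |
| Attempt first reported at week 1 or week 16 | yes | visit not tabulated | yes, if recorded as an AE |
| Attempt after the last completed interview, then withdrawal or loss, known from another contact | none | not counted | yes, if recorded as an AE |
| Death by suicide | none for the fatal event | not counted | yes, as serious |
| Attempt never known to the trial | none | not counted | no |

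Rows 3 and 4 are the point: the trial holds the event, but the endpoint does not. Row 2 is a related gap that the same remedy closes.

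**Step 2. Size.** The SAP states "we will enroll 20 participants", so one participant is 1/20 = 5 points. The event counts below are assumptions. The contrast is a cumulative any-event proportion, which the SAP does not currently plan; it is used only to show scale. Intervals are exact (Clopper-Pearson) 95%.

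| Assumed truth | Events without a score | Interviewed only | All sources, all 20 |
|---|---|---|---|
| 1 event | 1 | 0/19 = 0% (0 to 17.6%) | 1/20 = 5.0% (0.1 to 24.9%) |
| 2 events | 2 | 0/18 = 0% (0 to 18.5%) | 2/20 = 10.0% (1.2 to 31.7%) |
| 3 events | 1 | 2/19 = 10.5% (1.3 to 33.1%) | 3/20 = 15.0% (3.2 to 37.9%) |

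**Step 3. Direction.** Let p be the true proportion, q the share unscored, and RR the risk in unscored relative to scored youths. The scored youths then show p0 = p / ((1 − q) + q × RR). Assume p = 15% and q = 20%:

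- RR = 0.5: 0.15/(0.8 + 0.1) = 16.7%
- RR = 1: 0.15/(0.8 + 0.2) = 15.0%
- RR = 2: 0.15/(0.8 + 0.4) = 12.5%
- RR = 3: 0.15/(0.8 + 0.6) = 10.7%

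The result is too low only when RR exceeds 1. For a suicide death that is true by construction. For withdrawal and loss it is plausible but not given.

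**Step 4. What bounds would show.** Assume 2 known events. With 2 youths of unknown status, the interviewed-only figure is 2/18 = 11.1% and the bounds are 2/20 = 10% to 4/20 = 20%. With 4 unknown, it is 2/16 = 12.5%, with bounds of 2/20 = 10% to 6/20 = 30%.

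**The case against.** The strongest case against is that little is lost. A known suicide death or hospitalization is reported in the SAE summary, which in a study of 20 nobody would overlook. An attempter normally stays enrolled, and the since-last-contact form picks the attempt up at the next completed call. The study is descriptive, without formal comparisons (Protocol B.2.2), and the exact interval for 2/20, 1.2% to 31.7%, is far wider than a 5-point shift. Every input to the size is assumed. SAP 7 also refers reporting to SOPs that are not among the documents.

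Much of this stands. It limits the weight of the point and shows that the defect is two results left unreconciled, not events hidden from the report. It does not remove the gap: the endpoint can still omit an event that the trial knows about.

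Four stronger readings are tempting, and the documents do not support them:

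- *The C-SSRS is put only to the youth.* SAP 6.1.2 names no respondent, and a parent interview accompanies the calls, although it is not linked to C-SSRS scoring.
- *Readmission when a call is due leaves the youth unscored.* Protocol, Risk Management, asks staff to "schedule phone assessments at a time when the parent/guardian is present at the same location as the participant", and Enrollment Procedures notes that inpatients and parents are apart. The second remark concerns recruitment during the index admission, so the two do not conflict. Nothing bars a call during a readmission, and a later call can recover the event.
- *Withdrawn or lost youths are removed from the denominators by rule.* SAP 6.1.2 states no denominator, and such youths keep the scores already obtained.
- *The result is biased down in any case.* Step 3 shows that this depends on who is missing, and the lower bounds in Step 4 lie below the interviewed-only figures.

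**Conclusion.** The point holds in this form: the suicidal-behaviour endpoint has the C-SSRS as its sole named source and is reported only by visit at weeks 4, 8 and 12. A suicide death, or a documented attempt with no later C-SSRS because of withdrawal or loss, would therefore be in the AE/SAE tables and absent from the endpoint.

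The endpoint would be understated if youths with events are the ones missing, by about 5 points for each such youth at N = 20. That rests on assumed event counts and on event-related missingness. The actual size cannot be derived from the documents, which give no event rate and no loss rate during follow-up. The change should be made, but it is not critical: the endpoint is secondary and descriptive, and the events concerned, when known, are still reported as adverse events.

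**What to change.** In SAP 6.1.2:

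1. Keep the by-visit C-SSRS table, and add the number assessed and the reason missing at each visit.
2. Add a cumulative proportion with any suicidal behaviour, with all app-enrolled youths as the denominator. Count C-SSRS events from every scheduled post-baseline visit, plus death by suicide and any attempt documented in the AE/SAE record or in the parent and provider contacts already made.
3. Classify youths with incomplete follow-up and no known event as *status unknown*. Show the proportion with them scored as no event and again as event.
4. Footnote the source of each event.

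The cost is SAP wording, one derived variable and case-by-case classification of a few events from records. No new data collection is needed.

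The limits should be stated. The parent form records healthcare use rather than attempts. Provider contact is routine only at week 1 and otherwise depends on assessed risk. For a youth lost to follow-up these sources may be silent as well. They are not systematic ascertainment, which is why the unknown category and both bounds are needed.

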Recently, Drs. [name] and [name] conducted a feasibility open trial of BCBT in adult inpatients. Their findings suggest that BCBT may be a helpful intervention for adults hospitalized following a suicide attempt. Also recently, Sinyor et al. (2020) examined BCBT in youth hospitalized after an episode of suicidal behavior and despite small numbers, found a significant reduction in suicide behavior in the BCBT group. It is essential to examine whether this approach yields similar reductions in suicide re-attempt risk among adolescents, as well as whether this intervention can be delivered effectively via a smartphone app. We aim to build on their promising findings and extend this line of research to adolescent inpatients by developing a youth adapted version of our smartphone app product A [REDACTED] We will collect pilot feasibility data on [REDACTED] from this new population.

Specific Aim 1 – Create a beta version of [REDACTED] for youth (ages 13 - 17). Drawing on our experience in developing and implementing digital applications (i.e. "mobile apps" for Apple/Android devices) that have been shown to increase access to effective care for a variety of conditions (e.g. insomnia, anxiety, substance use) and are now available in benefit packages for over 50 million covered lives nationally, we will prepare the release of a beta version of A [REDACTED]. Creation of this beta version will constitute the bulk of the work to be accomplished in our proposed twelve-month Phase I project. [REDACTED]

Specific Aim 2 – To test the feasibility and acceptability of the beta version of [REDACTED] in a single-group, open-label trial. Following its creation, we will test the feasibility and acceptability of the Beta Version of [REDACTED] in a clinical sample of 20 adolescents (ages 13 - 17) who were recently admitted for suicidal ideation with a suicidal plan or report a lifetime suicide attempt. This will be done in a single-site, 16-week, single-group clinical trial. Feasibility and acceptability will be measured with logs and questionnaires.

Anticipated Outcome and Future Directions: [REDACTED]

BACKGROUND AND SIGNIFICANCE

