
summary reports, overseeing recruitment and enrollment and the execution of other research related tasks at IOL. Since this IRB approval will only cover the feasibility open trial, Drs. [name] and [name] are the only investigative team members listed as study personnel on the IRB application. For the feasibility open trial, Oui will not have direct contact with participants. Oui will provide technical support if needed, communicated by way of IRB-approved study staff at the ADC. Coded data from the feasibility open trial will be shared with Oui through a secure data transfer system (e.g., REDCap or password protected file sent via secure e-mail). In order to download the app, the participant will need to register directly with Oui. No PHI is required for app registration and download. The only data collected directly through the app is number of log ins and number of treatment modules completed. Oui's data and security for user information is detailed in the Data Security and Resource Sharing Plan section below. Oui has also signed a Business Associate Agreement with HHC (see attached).

INNOVATION

Several aspects of this application are novel. First, in the wake of the FDA's new guidance (2017) on mobile applications, this project attempts to capitalize on this guidance to address a great unmet need (reduction of youth suicide attempts). We are not aware of any other mobile technology attempting to address this issue in this way for youth. Second, the proposed project will lay the groundwork for a large, randomized clinical trial (RCT) powered to detect differences in rates of suicide attempts among youth recently discharged from a psychiatric hospital. Whereas most clinical trials in depression and related disorders are powered to detect differences in symptom severity or SI as measured by clinical rating scales, the next line of research following the successful completion of this project would use suicide attempts as a primary outcome. Third, the current project will involve feedback from multiple stakeholders, including patients, providers, administrators, and third-party payers. By considering the needs and perspectives of these various stakeholders, such an approach greatly enhances the likelihood that a clinically successful intervention will be adopted into clinical practice. Some additional innovative aspects of this project are outlined below.

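### SAP 6.1.2 tabulates the C-SSRS only by visit at weeks 4, 8 and 12, so it omits events reported at weeks 1 and 16 and cannot count distinct participants with suicidal behaviour.

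*SAP*

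**What the plan says.** - **SAP 6.1.2** gives the only planned C-SSRS output: results "for each question and within each of four constructs using counts and percentages over time", at weeks 4, 8 and 12. No row combines visits.
- **SAP 1.1.1** lists assessments at baseline and weeks 1, 4, 8 and 12. Week 1 is thus in the SAP's own schedule but not in its C-SSRS table.
- **Protocol, Timeline** has a lifetime C-SSRS at screening, then "Columbia Suicide Severity Rating Scale (C-SSRS) – since last contact" at weeks 1, 4, 8, 12 and 16. Under Specific Aim 2 the study is a 16-week trial: "This will be done in a single-site, 16-week, single-group clinical trial".
- **Protocol B.2.5** names suicide attempts and other behaviours as a secondary endpoint: "This outcome will be assessed via the Columbia Suicide Severity Rating Scale (CSSRS), which was designed to classify suicide attempts", along with aborted attempts and other suicidal behaviours. The secondary measures are "assessed using a within-group comparison, over time".
- **Protocol, Early Withdrawal of Participants** keeps a participant who attempts suicide in the study unless a withdrawal criterion is met.
- **SAP 5.1 and 5.2** count participants and events for AEs and SAEs by MedDRA system organ class and preferred term, within a reporting period.
- **Protocol, Innovation** says the next line of research "would use suicide attempts as a primary outcome".

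**The concern.** The follow-up windows are successive, and a participant can have an event in more than one of them. A table that treats each visit separately then counts visits with an event, not people with an event. Denominators shift as calls are missed, and an event in a missed interval moves to the next call that is answered. The visit percentages can be neither added nor averaged into a participant-level proportion.

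Two of the five collected contacts are also absent from the table. The week 1 contact covers the interval just after baseline and discharge. Protocol A.2 singles out the first month after discharge as the period with nearly half of that year's suicide deaths.

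At stake is whether the report can say how many of about 20 adolescents had an attempt or other suicidal behaviour while using the app. Every item needed is already collected. What is missing is the planned summary, its denominator and its rules.

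**Working it through.** **Inputs.** N = 20 app-enrolled participants (SAP 2; Protocol B.2.11). Protocol B.2.11 consents 22 to reach 20, which matches 20 × 1.10 = 22 (dividing instead gives 20 / 0.90 = 22.2). The documents give no attempt rate for this population, so there is no planned figure to reproduce, and all event counts below are assumptions.

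**Step 1: coverage.** Weeks are counted as in the timeline and every call is assumed made.

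| Contact | Window | Length (weeks) | C-SSRS collected | In SAP 6.1.2 |
|---|---|---|---|---|
| W1 | W0 to W1 | 1 | yes | no |
| W4 | W1 to W4 | 3 | yes | yes |
| W8 | W4 to W8 | 4 | yes | yes |
| W12 | W8 to W12 | 4 | yes | yes |
| W16 | W12 to W16 | 4 | yes | no |

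Tabulated: 3 + 4 + 4 = 11 of 16 weeks (69%). Not tabulated: 1 + 4 = 5 of 16 weeks (31%). For 20 participants with complete follow-up, that is 220 of 320 person-weeks tabulated and 100 not.

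**Step 2: missed calls.** If W4 is missed, the week 8 column holds a window of 8 − 1 = 7 weeks instead of 8 − 4 = 4. If W12 is missed, events from 16 − 8 = 8 weeks are first reported at W16 and enter no C-SSRS table.

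**Step 3: distinct participants.** For visit counts c1, c2, c3, the number D of distinct participants with an event reported at those visits satisfies

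max(c1, c2, c3) ≤ D ≤ min(N, c1 + c2 + c3).

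Assuming all 20 answer every call:

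| Assumed counts at W4 / W8 / W12 | D | Proportion of 20 |
|---|---|---|
| 1 / 1 / 1 | 1 to 3 | 5% to 15% |
| 2 / 1 / 1 | 2 to 4 | 10% to 20% |
| 2 / 2 / 1 | 2 to 5 | 10% to 25% |
| 2 / 2 / 2 | 2 to 6 | 10% to 30% |

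Exact (Clopper-Pearson) 95% limits for x of n are the 0.025 quantile of Beta(x, n − x + 1) and the 0.975 quantile of Beta(x + 1, n − x). For 2 of 20 they are 1.2% and 31.7%. For 6 of 20 they are 11.9% and 54.3%.

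These ranges concern the three tabulated visits only. The table says nothing about participants whose only event is reported at W1 or W16. If at most one tabulated visit shows events, or none does, D is fixed for those three visits, but W1 and W16 remain unseen.

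**Step 4: the AE tables as a substitute.** Protocol, AE Reporting treats suicidal thoughts and behaviours as expected AEs, and SAP 5.1 counts participants with an event. But Protocol B.2.9 elicits AEs by open questions about changes in physical and mental health, and the tables are by preferred term. No text links an event found on the C-SSRS to an AE record or maps C-SSRS classes to terms. The reporting period is not defined.

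**The case against.** **The protocol does not define a cumulative count.** This stands. A reader might infer that the number of distinct participants with an attempt is the written secondary endpoint. Protocol B.2.5 asks only for attempts and other behaviours over time within the group, and a by-visit table is a fair reading of that. It does not explain leaving out two collected contacts.

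**The AE and SAE tables may already give a count.** Partly stands. AEs are assessed at every contact, the AE tables are not limited to weeks 4, 8 and 12, and nothing says that an attempt disclosed on the C-SSRS is kept out of the AE record. The stronger reading, that the SAP as a whole cannot yield a count, is therefore not supported. The route is uncertain, and it would not reproduce the classes that Protocol B.2.5 names.

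**The next trial does not depend on this figure.** This stands. A reader might infer that the pilot's attempt rate will size the later trial. Protocol, Innovation only names attempts as that trial's outcome. The sentence on power calculations in Protocol B.2.11 follows text on completion and administration times. Every participant receives the app, so there is no control rate to carry forward.

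**The SAP may simply stop at week 12.** SAP 1.1.1 does end there, which could explain week 16, although the protocol collects it. It does not explain week 1.

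**Nothing is lost, and the sample is small.** The data exist and can be tabulated later, and the two intervals in the example overlap widely. But choosing classes, denominator and period after seeing a handful of events is what a SAP is meant to prevent.

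**Conclusion.** The concern holds as a gap in planned reporting, not in data collection. SAP 6.1.2 omits two of the five follow-up contacts at which the protocol collects the C-SSRS. Its by-visit layout cannot in general give the number of distinct participants with suicidal behaviour. With all calls made, 5 of 16 weeks (31%) are outside the table. In the assumed 2 / 2 / 2 case, the tabulated visits fit anything from 10% to 30% of 20 participants.

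The coverage figure rests on the protocol timeline. The 10% to 30% range rests on invented counts and full response, and it arises only when events occur at two or more tabulated visits. No decision rule in the documents turns on it, and the feasibility aims are unaffected. The change should be made before analysis because it settles what the trial can report on its most serious outcome.

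**What to change.** In SAP 6.1.2:

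1. Extend the per-visit table to W1, W4, W8, W12 and W16, with the number assessed at each, and align SAP 1.1.1 with the protocol timeline.
2. Add one row per behaviour class (suicide attempt, aborted attempt, other suicidal behaviour, any). Give the distinct participants with at least one event from baseline to last contact and the number of events. Use all app-enrolled participants as the denominator, with an exact 95% CI for the proportion.
3. Count any suicide death as an event even if no follow-up C-SSRS exists. A denominator limited to participants with a follow-up C-SSRS would lose a death before the first call.
4. Beside these rows, report the number with no follow-up C-SSRS, the number with complete follow-up and the person-weeks covered.

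The cost is a little extra programming on data already collected, with no new assessment. The interval goes beyond the counts and percentages in SAP 3 but remains descriptive. One limitation must be stated with the table: participants with partial follow-up count as event-free for the time not observed. The crude proportion is thus a lower bound on what complete follow-up would show, and the exact interval does not allow for this.
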